4. STUDY POPULATION

4.1. INCLUSION CRITERIA

At Visit 1 (Screening) and Visit 2 (Randomization) male or female subjects must meet the following criteria:

1. Provide written informed consent prior to any study-related procedures and provide Health Insurance Portability and Accountability Act (HIPAA) authorization.
2. Are 18 years of age or older.
3. Are willing and able to follow instructions and willing to be present for the required study visits for the duration of the study.
4. Have a BCVA, using corrective lenses if necessary, in the qualifying eye(s) of +0.7 or better as assessed by Early Treatment of Diabetic Retinopathy Study (ETDRS) at the screening visit and randomization visits.
5. If a woman of child-bearing potential (WOCBP) not pregnant or lactating and not sexually active (i.e. abstinent) for 14 days prior to Visit 1 and willing to remain so through 30 days following Visit 6 or the last administration of the IP. Alternatively, a WOCBP who is not abstinent must have been using acceptable methods of birth control.
6. Are women who have undergone one of the following sterilization procedures at least 6 months prior to Visit 1:
 - a. Bilateral tubal ligation
 - b. Hysterectomy
 - c. Bilateral oophorectomy
7. Have a history of dry eye disease in both eyes supported by a previous clinical diagnosis or have a self-reported history of subjective complaints for at least 6 months prior to screening
8. Are currently using artificial tears and have been using within 30 days of the screening Visit.
9. Have an Eye dryness score ≥ 40 at Visit 1 and ≥ 35 at Visit 2, one score for both eyes (0-100 point VAS)
10. Have ongoing dry eye disease in the same eye or both eyes, as defined by all of the following criteria at Visit 1 and Visit 2:
 - a. Inferior CFS (iCFS) score of ≥ 2 (NEI; 0-4 scale; using 0.5 unit increments)
 - b. Have a Schirmer score (without anesthesia) of ≥ 1 and ≤ 7 mm/5 min.
11. Have in the opinion of the Investigator, normal lid anatomy.
12. Are willing to withhold artificial tears for the duration of the study.

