- Occurrence of any AEs since the last visit *
- BCVA
- Slit-lamp biomicroscopy and external eye exam
 - Includes evaluation of conjunctival hyperemia
- CFS
- Wait 15-20 minutes after CFS before proceeding
- Unanesthetized Schirmer test
- IOP
- Collect used Run-In, Daily Dosing Diary and check compliance
- Determine if subject is eligible for randomization

For eligible subjects, the following is the process regarding administration of Double-Masked IP whereby the trained site staff will conduct the following procedures:

- Enter subject information into IWRS to determine randomization code and Kit Number.
- Subject will self-administer first dose of Double-Masked IP observed by trained study staff.
- Administer the Drop Comfort/Tolerability Assessment at 1-minute and 5-minutes post dose.

- Assess for occurrence of any IP related AEs
- Dispense 4 weeks supply of double masked IP and Daily Dosing Diary
- Collect used Single-Masked IP kit
- Schedule the subject to return for Visit 3 (Day 14±2 days)

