2.1.2. Study Eye

Subjects must replicate the following findings in the same eye at Visits 1 and 2 in order to be considered for further study eligibility: 1) Inferior CFS score ≥ 2 (0 - 4 scale) and 2) Schirmer score STT without anesthesia ≥ 1 and ≤ 7 mm, at Visit 1 and 2. If both eyes meet the two criteria above, the eye with the greater inferior CFS at Visit 2 will be selected as the study eye. If both eyes have an equal inferior CFS score at Visit 2, the eye with the lowest STT value at Visit 2 will be designated as the study eye. If both eyes have equal score in inferior CFS scores and equal STT values at Visit 2, the right eye (OD) will be selected as the study eye.

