2.4.2. Efficacy Variables

2.4.2.1. Primary Efficacy Endpoint

Mean Change from baseline (Visit 2) to Day 84 (Visit 6) in inferior region of CFS (iCFS) using the modified NEI/Industry Workshop (0-4 scale, using 0.5-unit increments)

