4.2.9. Visit Windows

Visit windows will be calculated based on the schedule of assessments in Table 1. Any visits or procedures performed outside the scheduled visits must be documented in the Unscheduled Visit page of the eCRF. Although there is a visit window of ± 2 days around the expected visit date, nominal visits will be used for the per-visit analyses for all the endpoints. In addition, for primary and key secondary efficacy endpoints, the unscheduled visit or early termination visit

Statistical Analysis Plan

Sponsor:	VivaVision Biotech, Inc.		
Protocol:	VVN001-CS-201		
Document Version No.:	V3.0	Document Date:	13-JAN-2022

will be mapped to the scheduled visit which is closest to the midpoint of two consecutive visit windows.

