4.7. Efficacy Evaluation

Efficacy analysis will be conducted using the FAS and PPS populations. All the following efficacy parameters will be analyzed as continuous variables and summarized at each follow-up timepoint (Day 0, Day 1, Day 14, Day 28, Day 56 and Day 84) using descriptive statistics (the number of subjects, mean, SD, median, minimum and maximum) by treatment group and overall. The absolute change from baseline (Day 1) to each follow-up timepoint (Day 14, Day 28, Day 56 and Day 84) in the following efficacy parameters will be also presented using descriptive statistics by treatment group. The two-sample T test under the assumption of normality of the efficacy endpoints will be utilized for comparing VVN001 5% versus vehicle and VVM001 1% versus vehicle at each follow-up timepoint. If the normality is not met, the Wilcoxon rank sum test will be performed instead.

Efficacy parameters:

- Total CFS score (0-20 scale)
- Individual subregion (inferior, superior, nasal, temporal, and central) of CFS score (0-4 scale)
- Schirmer test result without anesthesia (mm/5 min)
- Eye dryness VAS score (0-100)
- Discomfort VAS score (0-100)
- SANDE global score defined in Section 4.5.1

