4.7.1. Primary Analyses

The primary comparisons in this trial will be VVN001 5% versus vehicle and VVM001 1% versus vehicle on Day 84 in CFB of iCFS score on study eye. The repeated measures mixed model will be utilized to compare the treatment group. This method will assume that any missing data is Missing at Random (MAR). The repeated measures are the absolute change from baseline iCFS score obtained at the scheduled visit Day 14, 28, 56 and 84 respectively. The model will include treatment group (VVN001 5%, VVN001 1% and vehicle), baseline iCFS score, visit (Day 14, 28, 56 and 84), the interaction term of treatment \times visit as fixed effects, the center as a random effect.

SAS *PROC MIXED* with restricted maximum likelihood estimation (REML) and an unstructured (UN) within-subject covariance structure will initially be used. The sample SAS analysis code will use the following structure:

```
PROC MIXED DATA=indata;
  CLASS subject center visit treatment (REF='Vehicle');
```

Sponsor:	VivaVision Biotech, Inc.		
Protocol:	VVN001-CS-201		
Document Version No.:	V3.0	Document Date:	13-JAN-2022

```

MODEL change = treatment visit baseline_value treatment * visit
/Solution DDFM=KR;
  REPEATED visit / SUBJECT=subject TYPE=UN;
  RANDOM center;
  LSMEANS treatment treatment * visit / PDIFF CL;
  SLICE treatment * visit / SLICEBY=visit PDIFF CL;
RUN;

```

If the model fails to converge, compound symmetry (CS) will be implemented. From this model, the least squares mean (LSMEANS) for each treatment group and the estimated treatment differences for treatment comparisons will be presented together with 95% 2-sided confidence intervals for the differences and two-sided p-values for the treatment comparisons of the overall analysis. For assessments performed by eye, study eye and non-study eye will be summarized separately.

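### Could the mapping rule in SAP 4.2.9 place an exam from the first week of double-masked dosing on Visit 2 and so alter a subject's baseline?

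*SAP*

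**What the plan says.** SAP 4.2.9 has three parts.

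- Windows: "Visit windows will be calculated based on the schedule of assessments in Table 1". Table 1 lists Visit 2 as Day 1 with a tolerance of 2 days either way, and Visits 3 to 6 as Days 14, 28, 56 and 84 with the same tolerance.
- Per-visit analyses of all endpoints use nominal visits.
- As an addition, for the primary and key secondary endpoints only, an unscheduled or early-termination visit "will be mapped to the scheduled visit which is closest to the midpoint of two consecutive visit windows".

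Baseline is named by visit. SAP 2.4.2.1 has "Mean Change from baseline (Visit 2) to Day 84 (Visit 6", and SAP 4.7 has "The absolute change from baseline (Day 1) to each follow-up timepoint", the follow-up timepoints for change being Days 14, 28, 56 and 84. In SAP 4.7.1 baseline is a covariate, "MODEL change = treatment visit baseline_value treatment * visit", and the repeated responses come from the scheduled visits on Days 14, 28, 56 and 84.

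**The concern.** The mapping sentence compares a scheduled visit with a midpoint, and two neighbouring visits are equally far from the midpoint between them. A programmer therefore has to supply the rule. The obvious repair is to use the midpoints as cut-points on the actual study day. Two gaps then remain: Visit 2 is not excluded as a target, and nothing ranks a mapped value against a scheduled one.

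At Visit 2 the two values would always collide, because each randomized subject needs both scores there to qualify. For the signs, "Subjects must replicate the following findings in the same eye at Visits 1 and 2"; for the symptom, "Have an Eye dryness score ≥ 40 at Visit 1 and ≥ 35 at Visit 2". Neither document states that baseline is the last value before the first dose.

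Baseline is part of every change score and is also a covariate. If a post-dose value replaced it or was averaged with it, all of that subject's change scores would move, and the model would still run without complaint.

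**Working it through.** **1. The plan's own figures.** The SAP gives no cut-off days, so the mapping has no stated figure to reproduce. The yardsticks used below come from SAP 4.1: 55 per arm, differences of 0.43 (SD 0.80) and 13.75 (SD 25.5), and 80% power. With noncentrality (difference/SD) × √(55/2), 108 degrees of freedom and a two-sided 0.05 level:

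- iCFS: 0.5375 × 5.244 = 2.82, power 79.8%.
- Eye dryness: 0.5392 × 5.244 = 2.83, power 80.0%.

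The stated 80% reproduces.

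**2. Cut-points if Visit 2 is a target.** These use target days from Table 1; midpoints between window edges agree.

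| Pair | From target days | From window edges |
|---|---|---|
| Visits 2 and 3 | (1+14)/2 = 7.5 | (3+12)/2 = 7.5 |
| Visits 3 and 4 | (14+28)/2 = 21 | (16+26)/2 = 21 |
| Visits 4 and 5 | (28+56)/2 = 42 | (30+54)/2 = 42 |
| Visits 5 and 6 | (56+84)/2 = 70 | (58+82)/2 = 70 |

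Days 2 to 7 fall to Visit 2. Days 21, 42 and 70 are ties with no stated rule. If only post-baseline visits are targets, Days 2 to 20 fall to Visit 3 and nothing after Day 20 changes.

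**3. Which reading the rest of the text supports.**

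- The mapping serves two endpoints that are changes to Day 84, with model responses on Days 14 to 84. A post-dose exam mapped for such an endpoint is naturally a post-baseline record.
- The nominal-visit rule covers all endpoints, and baseline is itself a nominal visit.
- Protocol 6.1.3 to 6.1.6 count later visits from Visit 2 as Day 1, and Protocol 6.1.2 places Visit 2 at 14 days, give or take 2, after Visit 1. The tolerance on Visit 2 is a scheduling allowance after screening, not a period after randomization.
- Protocol 6.1.2 lists the symptom scores and corneal staining first, then the eligibility decision, and only then dosing: "For eligible subjects, the following is the process regarding administration of Double-Masked IP". The scheduled Visit 2 value is pre-dose by procedure.

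**4. Who could be affected.** A subject who terminates on Days 2 to 7 has no later visits, so there are no later change scores to distort. That leaves unscheduled visits in subjects who continue. Protocol 6.1.8 allows ophthalmic assessments at these but requires neither staining nor the VAS. Harm therefore needs an optional score in the first week, a subject who stays in the study, and an analyst who overrides the scheduled value unprompted.

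**5. Size if it happened to one subject.** Let the outcome have slope g on baseline B, and let baseline be replaced by B + d. The model residual of the change score moves by −g × d at each visit, so the arm mean moves by about g × |d| / 55. The following are assumptions, not figures from the documents: g from 0.3 to 0.7; |d| from 0.5 to 1.0 iCFS units or 10 to 30 VAS points.

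- iCFS: 0.3 × 0.5 / 55 = 0.0027, up to 0.7 × 1.0 / 55 = 0.0127. Against 0.43 that is 0.6% to 3.0%.
- Eye dryness: 0.3 × 10 / 55 = 0.055, up to 0.7 × 30 / 55 = 0.382. Against 13.75 that is 0.4% to 2.8%.

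Averaging the two values instead of replacing one halves d and so halves these shifts. The effect on the treatment difference grows with the imbalance between arms in the number of such subjects. A simulation of the iCFS case (3 × 55 subjects, four visits, SD 0.80, assumed correlation 0.5) gave mean shifts in the Day 84 difference of 0.0028 to 0.0123 at the two ends of the range, which agrees.

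**The case for a change.** The best case for rewriting the paragraph is that the sentence cannot be executed as written, that the repair costs one paragraph, and that silence allows a bad choice as well as a good one. SAP 4.7 even lists Day 1 among the timepoints to be summarized, so Visit 2 as a target is not absurd. SAP 4.2.8.2 ties adverse-event timing to the start of study drug, and the efficacy baseline has no such anchor. One consequence also needs no overwriting: a subject who leaves on Days 2 to 7 is in the SAP's FAS, and an exit exam labelled Visit 2 gives the mixed model no post-baseline row.

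Much of this stands as description. The sentence is defective, the ties are open and precedence is not stated. The lost exit row is a fair point, but it concerns at most one row per very early leaver, and the alternative lets an exam 7 to 12 days early stand for Day 14. Neither choice is clearly better.

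A rewrite also carries risk. Suppose a mapped exam were used only where the assigned visit is empty. An exit exam on Day 65, after an attended Day 56 visit, maps to Visit 5 and would be set aside. Unless the rule were confined to the mixed model, the LOCF analysis in SAP 4.7.1.1 would carry Day 56 forward in place of the true last observation.

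**Conclusion.** No change to the plan follows. This is a badly worded data-handling sentence that leaves a gap analysts fill sensibly: the scheduled pre-dose Visit 2 value is the baseline, and mapping serves the post-baseline visits. The nominal-visit rule, the visits named for the model and the order of procedures at Visit 2 all point that way, and nothing tells anyone to replace a baseline.

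The Days 2 to 7 result is correct arithmetic, but it rests on supplying a rule the SAP does not state and then counting Visit 2 as a target. Even on that reading, one overwritten baseline moves an arm's Day 84 mean by at most about 3% of the design difference, under the assumed slopes and shifts. The number of first-week exams is unknown from the documents, so no effect on the trial's result is shown.

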4.3. Interim Analyses

No interim analyses are planned for this study.

4.4. Subject Disposition

A tabulation of subject disposition will be tabulated for all screened subjects. The number of patients screened, and screened failure will be presented. The number and percentage of subjects included in each of the analysis populations (FAS, SAF, PPS) will be presented by treatment group and overall. Subject disposition events including randomization, treated, completed study, prematurely discontinued study and/or treatment, and reasons for premature study and/or treatment discontinuation will be summarized by treatment group and overall.

A by-subject listing of study completion information, including the reason for premature study withdrawal, if applicable, will be presented.

4.5. Demographic and Baseline Characteristics

Demographic characteristics and medical history information will be summarized for the FAS populations using descriptive statistics by treatment group and overall. Demographic characteristic information will include age (years), age category (<65 vs. ≥ 65), gender, ethnicity and race.

Age will be calculated as an integer by using SAS function: Floor ((randomization date – date of birth) /365.25).

No formal statistical comparisons will be performed.

Demographic and Baseline data will be provided in data listings.

4.5.1. Baseline Ocular Assessments

The following baseline assessments will be presented using descriptive statistics for FAS population by treatment group and overall.

The assessments below will have one score for both eyes per subject.

- Eye dryness VAS score (0-100)
- Discomfort VAS score (0-100)

Sponsor:	VivaVision Biotech, Inc.		
Protocol:	VVN001-CS-201		
Document Version No.:	V3.0	Document Date:	13-JAN-2022

- SANDE global score
 - The SANDE is comprised of two 100mm VAS scales. One measures frequency of symptoms from rarely (0) to all the time (100). The other measures severity of symptoms from very mild (0) to very severe (100). The global score is calculated as square root of the product of the two measurements.

The assessments below will be assessed for each eye including study eye and non-study eye, where study eye is defined in Section 2.1.2:

- Total CFS score (0-20 scale)
- Individual subregion (inferior, superior, nasal, temporal, and central) of CFS score (0-4 scale)
- Schirmer test result without anesthesia (mm/5 min)

4.5.2. Medical and Surgical History

Medical history, including ocular medical history, will be coded using the Medical Dictionary for Regulatory Activities (MedDRA version 23.0). Non-ocular medical history will be summarized in the FAS population by system organ class (SOC) and preferred term (PT) by treatment group and overall. SOC will be sorted alphabetically. PT will be sorted by descending frequency overall within each SOC. Subjects with a particular medical history event or medical history class will be counted once at the PT level and once at the SOC level. Ocular medical history will be summarized at the subject and eye levels by treatment group and overall in the FAS with separate summaries for the study eye and non-study eye.

Surgical history will not be coded in this trial and thus all data as collected in the CRF will be provided in data listings. Data listings will be provided for medical history as well.

4.6. Treatment Exposure

Details of study drug administration, including duration on treatment and extent of exposure will be tabulated and presented in the SAF population. The duration of exposure will be calculated in days as *last dose date-first dose date + 1* during the treatment period and summarized using descriptive statistics by treatment group and overall.

All dosing information will be presented in a data listing.

Statistical Analysis Plan

Sponsor:	VivaVision Biotech, Inc.		
Protocol:	VVN001-CS-201		
Document Version No.:	V3.0	Document Date:	13-JAN-2022

4.7. Efficacy Evaluation

Efficacy analysis will be conducted using the FAS and PPS populations. All the following efficacy parameters will be analyzed as continuous variables and summarized at each follow-up timepoint (Day 0, Day 1, Day 14, Day 28, Day 56 and Day 84) using descriptive statistics (the number of subjects, mean, SD, median, minimum and maximum) by treatment group and overall. The absolute change from baseline (Day 1) to each follow-up timepoint (Day 14, Day 28, Day 56 and Day 84) in the following efficacy parameters will be also presented using descriptive statistics by treatment group. The two-sample T test under the assumption of normality of the efficacy endpoints will be utilized for comparing VVN001 5% versus vehicle and VVM001 1% versus vehicle at each follow-up timepoint. If the normality is not met, the Wilcoxon rank sum test will be performed instead.

Efficacy parameters:

- Total CFS score (0-20 scale)
- Individual subregion (inferior, superior, nasal, temporal, and central) of CFS score (0-4 scale)
- Schirmer test result without anesthesia (mm/5 min)
- Eye dryness VAS score (0-100)
- Discomfort VAS score (0-100)
- SANDE global score defined in Section 4.5.1

4.7.1. Primary Analyses

The primary comparisons in this trial will be VVN001 5% versus vehicle and VVM001 1% versus vehicle on Day 84 in CFB of iCFS score on study eye. The repeated measures mixed model will be utilized to compare the treatment group. This method will assume that any missing data is Missing at Random (MAR). The repeated measures are the absolute change from baseline iCFS score obtained at the scheduled visit Day 14, 28, 56 and 84 respectively. The model will include treatment group (VVN001 5%, VVN001 1% and vehicle), baseline iCFS score, visit (Day 14, 28, 56 and 84), the interaction term of treatment \times visit as fixed effects, the center as a random effect.

SAS *PROC MIXED* with restricted maximum likelihood estimation (REML) and an unstructured (UN) within-subject covariance structure will initially be used. The sample SAS analysis code will use the following structure:

```
PROC MIXED DATA=indata;
  CLASS subject center visit treatment (REF='Vehicle');
```

Sponsor:	VivaVision Biotech, Inc.		
Protocol:	VVN001-CS-201		
Document Version No.:	V3.0	Document Date:	13-JAN-2022

```

MODEL change = treatment visit baseline_value treatment * visit
/Solution DDFM=KR;
  REPEATED visit / SUBJECT=subject TYPE=UN;
  RANDOM center;
  LSMEANS treatment treatment * visit / PDIFF CL;
  SLICE treatment * visit / SLICEBY=visit PDIFF CL;
RUN;

```

If the model fails to converge, compound symmetry (CS) will be implemented. From this model, the least squares mean (LSMEANS) for each treatment group and the estimated treatment differences for treatment comparisons will be presented together with 95% 2-sided confidence intervals for the differences and two-sided p-values for the treatment comparisons of the overall analysis. For assessments performed by eye, study eye and non-study eye will be summarized separately.

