4.4. STUDY EYE

Subjects must replicate the following findings in the same eye at Visits 1 and 2 in order to be considered for further study eligibility: 1) Inferior CFS score ≥ 2 (0 – 4 scale) and (2) Schirmer score STT without anesthesia ≥ 1 and ≤ 7 mm, at Visits 1 and 2. If both eyes meet the two criteria above, the eye with the greater inferior CFS at Visit 2 will be selected as the study eye. If both eyes have an equal inferior CFS score at Visit 2, the eye with the lowest STT value at Visit 2 will be designated as the study eye. If both eyes have equal score in inferior CFS scores at Visit 2, the right eye (OD) will be selected as the study eye.

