2.2. Randomization Methodology

Approximately 165 subjects will be randomized by permuted block in this study at approximately 10 centers located in the United States. Subjects will be randomized to one of the following 3 treatment groups VVN001 1%, 5% or Vehicle in a 1:1:1 ratio.

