4. STATISTICAL METHODS

4.1. Sample Size Justification

A sample size of 55 subjects per treatment group will have 80% power to detect a treatment difference of 0.43 units with a common standard deviation 0.80 in iCFS score, and a treatment difference of 13.75 units with a common standard deviation 25.5 in eye dryness score at Visit 6/Day 84 using a t-test with a 0.05 two-sided significance level.

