4.2.4. Adjustments for Covariates

Analyses of the change from baseline in primary and secondary efficacy endpoints utilizing repeated measures mixed model will adjust for the baseline score of the parameter of interest as a continuous covariate, treatment group as the main effect, and visit as a repeated measure on subject in the model.

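### The Visit 2-only mixed model is valid, but adding the Visit 1 score as a second baseline covariate would probably gain a little precision at negligible cost

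*SAP*

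**What the plan says.** SAP 4.2.4 states that the primary and secondary models "will adjust for the baseline score of the parameter of interest as a continuous covariate". SAP 4.7.1 gives the iCFS model: treatment, "baseline iCFS score, visit (Day 14, 28, 56 and 84"), the treatment-by-visit interaction, and center as a random effect. SAP 4.7.2 repeats the structure for the secondary endpoints. Both sample PROC MIXED programs, and the PROC GLM program for the LOCF sensitivity analysis in 4.7.1.1, carry one baseline term. Protocol 9.1.3 likewise names a single baseline covariate, and SAP 2.4.2 takes change from Visit 2.

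Protocol 6.1.1 and Appendix 1 schedule corneal staining, the dryness and discomfort VAS, SANDE and Schirmer at Visit 1 as well, with ocular tests in both eyes. For the study eye, Protocol 4.4 says "Subjects must replicate the following findings in the same eye at Visits 1 and 2", the findings being the iCFS and Schirmer criteria. Eye dryness has a threshold at each of the two visits (Protocol 4.1). Total staining, the other staining subregions, discomfort and SANDE are measured at Visit 1 but are not eligibility criteria.

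The sample size (SAP 4.1) reads: "A sample size of 55 subjects per treatment group will have 80% power to detect a treatment difference of 0.43 units", with "common standard deviation 0.80 in iCFS score", and a "treatment difference of 13.75 units with a common standard deviation 25.5 in eye dryness score", "using a t-test with a 0.05 two-sided significance level".

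**The concern.** Each pre-randomization score is a single noisy reading: a half-grade rating by the investigator, or one mark on a line. Two such readings usually estimate a subject's underlying severity better than one, and a covariate that predicts the Day 84 outcome better leaves less residual variance. The second reading exists for iCFS, Schirmer and eye dryness in every correctly enrolled subject, and is scheduled for the other parameters.

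What is at stake is modest precision at the top of a fixed sequence. SAP 4.2.5 stops testing at the first p-value above 0.05, so the 5% versus vehicle comparison on iCFS gates everything after it. The sample size calculation states no dropout allowance, and withdrawals are not replaced (SAP 4.2.7).

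**Working it through.** **Inputs from the documents.** 55 per arm; iCFS difference 0.43, SD 0.80; eye dryness difference 13.75, SD 25.5; two-sided 0.05 (SAP 4.1). Allocation is "VVN001 1%, 5% or Vehicle in a 1:1:1 ratio" (SAP 2.2), so N = 3 × 55 = 165. iCFS must be at least 2 at both visits, on a 0 to 4 scale in steps of 0.5 (Protocol 4.1). The documents give no correlation among Visit 1, Visit 2 and Day 84, so every correlation below is an assumption.

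**Step 1: the plan's own figure.** n = 2 × [(1.960 + 0.842) × SD / difference]².
- iCFS: 2 × (2.802 × 0.80 / 0.43)² = 54.3, so 55 per arm. Power at 55 is 80.5% by the normal approximation and 79.8% by the exact noncentral t.
- Eye dryness: 54 per arm by the same formula; exact power at 55 is 80.0%.

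The stated figures are reproduced.

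**Step 2: what a second covariate does.** Let r1 and r2 be the correlations of Visit 1 and Visit 2 with Day 84, and r12 the correlation between the two visits. The residual variance, relative to the raw variance, is
- Visit 2 only: 1 − r2²
- both visits: 1 − (r1² + r2² − 2·r1·r2·r12) / (1 − r12²)

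Their ratio is multiplied by 160/159 for the extra estimated coefficient. With all three correlations equal to ρ, the two expressions become 1 − ρ² and 1 − 2ρ²/(1 + ρ):

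| ρ (assumed) | Visit 2 only | Both | Ratio × 160/159 | Change in SE |
|---|---|---|---|---|
| 0.3 | 0.910 | 0.862 | 0.953 | −2.4% |
| 0.5 | 0.750 | 0.667 | 0.894 | −5.4% |
| 0.7 | 0.510 | 0.424 | 0.836 | −8.6% |

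If Visit 1 carries nothing beyond Visit 2 (r1 = r12 × r2), the ratio is 1.006 and the SE is 0.3% larger. Simulating 3 × 55 complete cases gave variance ratios of 0.955, 0.897 and 0.843 for the three rows and 1.006 to 1.011 for the redundant case. Type I error with both scores was 4.8% to 5.2%.

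**Step 3: allow for the eligibility cut.** Step 2 is too generous for iCFS, because both readings are truncated at 2 and rounded to half grades. Simulations that impose this gave:
- latent correlation 0.3 to 0.7, latent mean 1.5 to 2.75, SD 0.8, no drift: SE lower by 0.6% to 6.6%;
- latent severity drifting over time, reliability 0.40 to 0.70: variance lower by 1.2% to 9.5%, mid-range about 2.5% to 5%;
- also choosing the eye with the greater Visit 2 iCFS: variance lower by 0.7% to 11.8%, and by 1.4% to 4.9% at a latent Visit 2-to-Day 84 correlation of 0.8;
- Visit 1-to-Day 84 latent correlation 30% lower (latent mean 2.25): SE between 0.3% lower and 0.3% higher;
- drift, with center in the model (10 sites assumed, carrying 30 to 50% of between-subject variance): variance lower by 1% to 3%, against 2.5% to 6% without center.

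The cut shrinks the gain but does not remove it.

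**Step 4: translate into power.** Take 0.80 as the residual SD of the planned model. The residual SD with both scores is then 0.80 × √(variance ratio), and exact t power at 55 per arm is:

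| Variance ratio | Power | Equivalent n per arm (55 × ratio) |
|---|---|---|
| 1.006 | 79.5% | 55.3 |
| 1.000 | 79.8% | 55.0 |
| 0.990 | 80.2% | 54.5 |
| 0.975 | 80.8% | 53.6 |
| 0.950 | 81.8% | 52.3 |
| 0.900 | 83.8% | 49.5 |

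The Day 84 comparison with complete data stands in for the full mixed model throughout.

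**The case against.** The strongest reply is that nothing is wrong. The endpoint defines baseline as Visit 2, the protocol names one covariate, the SAP follows it, and the test is valid. All of that stands.

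A reader might infer that the extra covariate is certain to raise precision and has no downside. The documents do not support this. Visit 1 is not a replicate of Visit 2: subjects arrive as current artificial-tear users, then stop prohibited medications and take vehicle for 14 days before Visit 2, so Visit 2 is measured under conditions closer to the treatment period. With no correlation reported, a gain of zero is possible, and then the SE is slightly larger. The random center effect may also already absorb part of what Visit 1 would explain.

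A reader might also infer that the trial is short of power without this change. That is not established. SAP 4.1 does not say whether 0.80 is the SD of the raw score, of the change or of the residual, and its t-test uses no covariate. If 0.80 is the raw SD and all correlations are 0.3, Visit 2 adjustment alone gives 84.0% power (normal approximation), and both scores give 85.7%.

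Finally, it would be wrong to say that eligibility requires two readings of every efficacy parameter. It does so only for iCFS, Schirmer and eye dryness. For the others the Visit 1 value is scheduled, but its added value has not been sized here.

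**Conclusion.** A cheap improvement, not a correction of an error. The likely reduction in iCFS residual variance at Day 84 is about 0 to 10%, most plausibly 1 to 5%. That is worth roughly 0.5 to 3 subjects per arm in the plausible range, or 80 to 82% power against 79.8%, with 84% at the 10% end. The larger reductions in some no-drift simulations are an optimistic bound, since they ignore the change of conditions between Visit 1 and Visit 2. The power figures assume that 0.80 is the residual SD; the variance figures rest on assumed correlations. The balance still favors the change, because the worst case is an SE about 0.3% larger and type I error is unaffected.

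**What to change.** Before unmasking:

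- In SAP 4.2.4, 4.7.1 and 4.7.2, add the Visit 1 value of the same parameter as a second continuous covariate, taken from the same eye for per-eye measures.
- Add the same term to the LOCF ANCOVA in 4.7.1.1, so that the sensitivity analysis adjusts for the same baseline scores as the primary model.
- Keep Visit 2 as the reference for change, so the endpoint definition does not move.
- Record the addition in SAP section 5, which currently reports no departures from the protocol's analyses, because Protocol 9.1.3 names one baseline covariate.

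If the sponsor prefers to leave the primary model as it is, the two-covariate model can be prespecified as a supportive analysis.

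The cost is one degree of freedom, one term in each program and a short SAP revision. No new data are needed, and by its title Table 14.1.5 already reports ocular findings at screening.
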